1 INTRODUCTION

This Statistical Analysis Plan (SAP) is based on Protocol GTII503 Version 3.0, dated 21 Mar 2017. The purpose of this SAP is to ensure that the statistical methodologies that will be used, and the data listings, summary tables and figures which will be produced, are appropriate and complete to support valid conclusions regarding the study objectives and the completion of Clinical Study Report (CSR). Additional post-hoc or unplanned analyses, which are not defined in this SAP, may be performed to support the clinical development program. Such analyses will be documented in the CSR.

2 STUDY DESIGN AND OBJECTIVES

2.1 Study Design

This is a prospective, multi-center, open-label, single-arm, efficacy, pharmacokinetic (PK), safety and tolerability study of Immune Globulin Subcutaneous (Human), 20% Caprylate/Chromatography Purified (IGSC 20%) in subjects with primary immunodeficiency (PI). Approximately 60 subjects will be enrolled in order to have approximately 20 adult subjects (> 16 years) and 20 pediatric subjects (\leq 16 years) treated with subcutaneously (SC) administered IGSC 20% who complete the entire study. This study will include 3 study stages: Screening/Previous Regimen Phase, IGSC 20% Treatment Stage 1 (13 IGSC 20% weekly doses), and IGSC 20% Treatment Stage 2 (39 IGSC 20% weekly doses).

Subjects who are receiving intravenous immune globulin (IVIG) at a dose of at least 200 mg/kg per infusion every 3 or 4 weeks at Screening must be on a stable Immunoglobulin G (IgG) regimen (dose and dosing interval) for at least 3 consecutive months prior to Screening. Subjects who are receiving subcutaneously delivered immune globulin (SCIG) must also be on a stable regimen for at least 3 consecutive months prior to Screening; there is no prerequisite minimum dose for subjects entering study on an SCIG regimen. Subjects who have never received IVIG or SCIG treatment (treatment naïve) will not be eligible for entry into the study.

Previous Regimen Phase:

- Subjects will be infused with their current ongoing (“previous regimen”) IVIG/SCIG regimen (pIV/pSC) in the clinic (mandatory) to obtain 2 trough IgG levels (obtained prior to each pIV/pSC infusion) on each subject’s “previous regimen”. For subjects entering study on SCIG, the second IgG trough level may be obtained at Baseline, immediately prior to starting the initial infusion of IGSC 20%.
- The Screening Visit may coincide with the pIV/pSC infusion on the previous regimen (pIV#1/pSC#1). Product for the previous IgG regimen is not provided by Grifols. pIV subjects will be enrolled in IGSC 20% Treatment Stage 1 one week after completion of the last IgG trough sampling in the Previous Regimen Phase and therefore the subject must have 2 minimum concentration (C_{trough}) samples on their pIV **prior** to the Baseline/Week 1 visit. pSC subjects will be enrolled in IGSC 20% Treatment Stage 1 (Baseline) in accordance with the time interval that they are currently receiving SCIG (ie,

if on a weekly SCIG regimen, Baseline will occur 1 week after completion of the last SCIG infusion and a second IgG trough level will be obtained at Baseline. If the interval between pSC infusions is 2 weeks (or more), then Baseline will occur after that time interval has elapsed, a trough IgG level will be obtained, and the eligible subject may commence IGSC 20% after Baseline assessments are complete).

- Nonconsecutive C_{trough} samples are acceptable for subjects on SCIG. A minimum of 10 days is anticipated for the Screening/Previous Regimen Phase to ensure Screening human immunodeficiency virus (HIV) nucleic acid amplification technology (NAT) test results will be available before the Baseline Visit/Week 1 visit.

20% IGSC Treatment Stage 1:

- The first dose of the investigational product (IP), IGSC 20%, will be administered immediately after Baseline assessments are complete (SC#1). Subjects will be infused with IGSC 20% at a 1:1 dose-equivalent regimen (per equation in Section 3.3.2 of the protocol) from their previous regimen at the clinical site (or a minimum IGSC 20% dose of 100 mg/kg/week if the derived 1:1 dose from the previous regimen is lower).
- All subjects will receive 13 IGSC 20% infusions at weekly intervals and study visits at the clinical site will occur at Baseline/SC#1, SC#2, #3, #5, #9, and #13. IgG trough blood levels will be measured at all of these visits (except SC#3) occurring at the clinical site. All other doses of IGSC 20% may be infused at home (once properly trained) or in the clinic.
- The mg/kg dose of IGSC 20% (ratio of mg per kg) will be adjusted at clinic visits if the trough level in subjects is below 500 mg/dL, a level that is considered as insufficient to protect against serious bacterial infection (SBI); the goal is to avoid repeated dose adjustments. The precise dose adjustment (mg/kg) should not be more than a 15% to 20% increase from the dose producing low IgG trough, per the Investigator's discretion. Any dose adjustments beyond this range will be completed in consultation with the Grifols Medical Monitor. The Treatment Stage 1 dose will continue into IGSC 20% Treatment Stage 2. After the 13th IGSC 20% infusion in IGSC 20% Treatment Stage 1, subjects will enter IGSC 20% Treatment Stage 2 to receive an additional 39 weeks of IGSC 20% therapy.

IGSC 20% Treatment Stage 2:

[figure not shown]
- The IGSC 20% dose (mg/kg) will remain constant with no dose adjustment permitted in this phase, unless it is absolutely medically necessary to change the dose, and such change requires prior consultation with the Grifols Medical Monitor. Dosing will be based on the subject's most current weight. For the subsequent at home IGSC 20% infusions between clinic visits, the dose will be the same as the total infusion dose calculated at the previous clinic study visit where weight was measured at the clinical site.
- While all subjects will have a SC#17 clinic visit and standard assessments, serial PK sampling will only be performed in a subset of adult subjects: At SC#17, PK profiles in

the first (where possible) 20 adult subjects, will be measured by obtaining blood draws for steady-state PK analyses over a period of 7 days just prior to and post the 17th IGSC 20% infusion through SC#18. These subjects will constitute the PK subset in this study.

- Where possible, the PK subset will comprise the first 20 adult subjects enrolled. Any designated PK subject who undergoes a dose adjustment (mg/kg change in dose) at or after the ninth IGSC 20% infusion (SC#9) which corresponds to at or after Week 9 in Treatment Stage 1 will be permitted to continue within the study, though he/she will not participate in PK profiling; however, an additional PK replacement subject may be recruited.
- Similarly, PK subjects who do not complete the full PK profile may be replaced if deemed necessary.

A total of 52 doses of IGSC 20% will be administered (13 doses of IGSC 20% in Treatment Stage 1 and 39 doses of IGSC 20% in Treatment Stage 2) with a final follow-up visit at Week 53 one week after the last dose at Week 52.

The overall study schema and the specific time points for PK sampling for Previous Regimen Phase and IGSC 20% Treatment Stages are outlined in Figure 2-1, and the schedule of study procedures, PK details, and definitions for the primary endpoint variable, SBIs are provided in Appendix 1 to Appendix 3 of the protocol.

¹ Screening Visit may coincide with the first IV infusion on previous regimen

² C_{trough} at baseline (prior to the first IGSC 20% infusion) is also the second trough level of IgG for the previous SC regimen

³ pIV or pSC indicates the previous regimen (only in the Previous Regimen Phase)

Note: Clinical visits for all subjects include Screening Visit, Final Visit, and all time points designated by C_{trough} as shown above.

Figure 2-1 Overall Study Schema

2.2 Study Objectives

2.2.1 Efficacy and Pharmacokinetic Objectives

2.2.1.1 Primary Efficacy Objective

The primary objective of this Phase 3 study is to evaluate whether weekly administered IGSC 20% over a one year period will achieve less than 1 SBI per subject per year in PI subjects.

2.2.1.2 Secondary Objectives

- To determine if IGSC 20% replacement therapy maintains mean trough IgG levels that are comparable to the mean trough blood levels with the previous IgG replacement regimen
- To evaluate all infections of any kind (serious/nonserious including acute sinusitis, exacerbation of chronic sinusitis, acute otitis media, pneumonia, acute bronchitis, infectious diarrhea, etc.) as determined by the Investigator
- To evaluate number of days on antibiotics (including oral, parenteral, oral plus parenteral, prophylactic, and therapeutic). Use of prophylactic antibiotics will be distinguished from antibiotics for treatment of acute infection.
- To evaluate number of hospitalizations due to infection
- To evaluate number of days of work/school/daily activities missed per subject year due to infections and related treatment

2.2.1.3 Other Objectives

- To evaluate trough levels of IgG subclasses (IgG1, IgG2, IgG3, IgG4)
- To evaluate antibody levels for *Streptococcus pneumoniae*, *Hemophilus influenzae*, and *Clostridium tetani* (tetanus)
- To evaluate the PK profile for total IgG (area under the concentration-time curve from 0 to 7 days [AUC_{0-7 days}], maximum concentration [C_{max}], and time to reach C_{max} [t_{max}]) in adult PI subjects at steady state (after approximately 4 months [16 weeks]) of weekly administration of IGSC 20%
- Trough measles antibody titers (functional assay) are an exploratory variable for informational purposes
- To evaluate validated infections documented by positive radiograph, fever (> 38°C oral or > 39°C rectal), culture, *or* diagnostic testing for microorganisms eg, bacterial, viral, fungal, or protozoal pathogens (for instance, rapid streptococcal antigen detection test).

2.2.2 Safety Objectives

- To assess the safety and tolerability of IGSC 20% as an IgG replacement therapy in subjects with PI.

3 STUDY VARIABLES

3.1 Efficacy and Pharmacokinetic Variables

3.1.1 Primary Efficacy Variable

The primary efficacy variable is the number of SBIs. Also, the percentage of subjects with SBIs will be summarized. SBI definitions (Food and Drug Administration [FDA]/European Medicines Agency [EMA] diagnostic criteria) are provided in Appendix 3 of the protocol.

3.1.2 Secondary Variables

One of the secondary endpoints of this study is trough concentrations of total IgG of previous regimen during the Screening/Previous Regimen Phase and the IGSC 20% Treatment Stages. It is measured to determine if IGSC 20% replacement therapy maintains mean trough IgG levels that are comparable to the mean trough blood levels with the previous IgG replacement regimen.

Other secondary variables include the rate of infection of any kind (serious and non-serious), antibiotic treatment (oral, parenteral, oral plus parenteral, prophylactic, and therapeutic), hospitalizations due to infection, and days lost from work/school/daily activities due to infections and related treatment. The infection of any kind includes acute sinusitis, exacerbation of chronic sinusitis, acute otitis media, pneumonia, acute bronchitis, infectious diarrhea, etc., which will be recorded as an AE with the Investigator answering the following question affirmatively in the eCRF: “Is this an infection?” (verbatim term delineating nature of infection).

3.1.3 Other Variables

Additional PK parameters include average trough concentration of IgG subclasses (IgG1, IgG2, IgG3, and IgG4), and concentration of antibody levels to *S. pneumoniae*, *H. influenzae*, and *C. tetani* (tetanus). Trough measles antibody titers (functional assay) are an exploratory variable for informational purposes.

For the adult (n~20) PK subset, serial samples will be collected immediately before and after SC#17 infusion at steady state. The PK profile will include total IgG concentrations at timepoints over a 7-day period. PK parameters including $AUC_{0-7days}$, C_{max} , and t_{max} will be determined by a noncompartmental model using WinNonlin.

Another efficacy variable is validated infections documented by positive radiograph, fever ($> 38^{\circ}C$ oral or $> 39^{\circ}C$ rectal), culture, or diagnostic testing for microorganisms eg, bacterial,

viral, fungal, or protozoal pathogens (for instance, rapid streptococcal antigen test) will be analyzed separately.

3.2 Safety Variables

The following safety variables will be assessed in this study:

- AEs, suspected adverse drug reactions (suspected ADRs), serious AEs (SAEs), and discontinuations due to AEs and SAEs
Note: All infusion site reactions will be recorded in the eCRF. The subset of infusion site reactions where the symptoms/signs lead to infusion interruption or discontinuation, require concomitant medication, or have an impact on the general condition of the subject as judged by the Investigator will be considered as AEs.
- Vital signs during clinic visits (temperature [T], respiratory rate [RR], heart rate [HR], systolic blood pressure [SBP] and diastolic blood pressure [DBP]).
- Physical assessments: physical exams will be recorded as normal or abnormal, according to the physician's judgment criteria, and findings will be recorded.
- Laboratory assessments including chemistry, hematology, and urinalysis.

4 GENERAL STATISTICAL CONSIDERATIONS

Statistical analyses and data presentations will be generated using SAS version 9.4 or higher.

Unless otherwise noted, for continuous variables, descriptive statistics will include the number of non-missing values, mean, standard deviation (SD), median, minimum and maximum. For categorical variables, descriptive statistics will include counts and percentages per category. The hypothesis testing on the primary efficacy variable of the true rate of the SBIs will be tested at 1-sided with $\alpha=0.01$. All other statistical inferences will be tested at 2-sided with $\alpha=0.05$, if applicable.

Unless otherwise noted, all data collected in the eCRFs or electronically transferred (such as central laboratory data) will be presented in data listings. Subjects will be identified in the data listings by subject number (which includes site number) and grouped/sorted by adult vs. pediatric subjects, followed by study phases (Screening/Previous Regimen Phase, IGSC 20% Treatment Stage 1, and IGSC 20% Treatment Stage 2) and visit/time point.

For table summaries, the data will be presented at the scheduled visits according to protocol. Any data collected at the unscheduled visits will be listed.

For table summaries that are presented by adult vs. pediatric subjects and overall, the following age categorization will be used: adults (>16 years) and pediatrics (≤ 16 years).

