3.6.2 Observations and Measurements

The following sections describe the procedures/assessments to take place at each study visit. See the Schedule of Study Procedures table in [Appendix 1](#) for a summary of study visits and the procedures to be conducted at each visit. Visits occurring after the Baseline Visit should be scheduled at the protocol-specified week relative to the date of the Week 1 (Baseline) Visit; a ± 1 day window is allowed with the exception of the serial PK sampling (non-dosing) visits (only applicable to the PK subset). If there are logistical issues requiring schedule adjustment for weekly IGSC 20% administration, SC#1 may be scheduled 6 to 9 days after pIV#2. Schedule adjustment may also be made after SC#3 or later (± 2 days from last infusion) when home infusion is initiated. Unscheduled visits may be conducted if deemed necessary for the purpose of subject safety.

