- ^g Laboratory Assessments (chemistry, hematology, haptoglobin, & urinalysis) will be performed at the Screening and Baseline Visits. Additional testing of all laboratory assessments will be prior to IGSC 20% infusion clinic visits coinciding with SC#13, #24, and #36, and the Final Visit. Laboratory testing includes **Hematology**: Hemoglobin, hematocrit, platelets, red blood cell count including red blood cell morphology, white blood cell count with differential; ARC. **Additional Special Tests**: DAT, serum free hemoglobin, haptoglobin (during Screening and Baseline, only haptoglobin will be measured. At all other time points specified, all additional special tests will be performed). **Chemistry**: Sodium, potassium, creatinine, chloride, calcium, BUN, bicarbonate, albumin, LDH, AST, ALT, ALP, glucose, total bilirubin, indirect bilirubin. **Urinalysis**: pH, protein, glucose, ketones, bilirubin, nitrites, urobilinogen, blood, leukocyte esterase (with microscopic examination of urine sediment if abnormal).
- ^h Potential child-bearing females only; results must be negative to participate in the study or continue on IP. Qualitative serum β -HCG will be performed at Screening Visit and repeated during the Screening/Previous Regimen Phase for subjects entering study on a prior IVIG regimen who do not have Screening Visit and pIV#1 coincide (pre-dose pIV#1) given the potential for an 8-week time interval before Baseline. A qualitative urine pregnancy test will be performed at Baseline at the investigative site.
- ⁱ Collect blood samples at Baseline, prior to IGSC 20% infusion but test *only* if the subject exhibits clinical signs and symptoms consistent with hepatitis A, hepatitis B, hepatitis C, HIV, or parvovirus B19 infection while participating in the study. See [Section 3.6.3](#) and [Table 3-1](#) for details. **Note: For young pediatric subjects, at the discretion of the Investigator, virus safety retain samples may be drawn the day prior to Baseline instead of combining with other baseline blood draws on a single day.**
- ^j During Treatment Stage 1 and Treatment Stage 2 IGSC 20% infusions will be given in the clinic with observation of self-administration technique (subject/caregiver) of SC infusion at Visit Designations SC#1, 2, 3, 5, 9, 13, 17, (18 for PK subset), 20, 24, 28, 32, 36, 40, 44, 48, and 52. The remaining weekly IGSC 20% doses should be administered at home.

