11.2 Laboratory Assessments

Hematology (hemoglobin, hematocrit, platelets, red blood cell count including red blood cell morphology, white blood cell count with differential, absolute reticulocyte count [ARC]), clinical chemistry (sodium, potassium, creatinine, chloride, calcium, blood urea nitrogen [BUN], bicarbonate, albumin, lactate dehydrogenase [LDH], aspartate aminotransferase [AST], alanine aminotransferase [ALT], alkaline phosphatase [ALP], glucose, total bilirubin, indirect bilirubin), special tests (direct antiglobulin test [DAT], serum free hemoglobin, haptoglobin), serum pregnancy test, and urinalysis (pH, protein, glucose, ketones, bilirubin, nitrites, urobilinogen, blood, leukocyte esterase [with microscopic examination of the urine if abnormal]) will be collected for all subjects if applicable at the assigned visits according to the protocol. The urine pregnancy test performed at Baseline/SC#1 for the determination of subjects' eligibility will be analyzed locally at the investigative sites. All other laboratory panels above will be stored and/or analyzed by a central laboratory.

The hematology, clinical chemistry, special tests, serum pregnancy, and urinalysis parameters will be summarized at each visit with number of subjects, mean, SD, median, minimum, and maximum values for continuous variables and counts and percentages per category for categorical variables. Change from baseline will be descriptively summarized

for continuous variables. Shift tables, based on the high/low flags, will also be summarized at each visit for each parameter with normal ranges. For selected analytes, tabular summaries and listings will be provided of treatment-emergent laboratory abnormalities utilizing the following thresholds of interest which are in some cases relative to the established reference range (multiples of lower limit of normal [LLN] or upper limit of normal [ULN]) and in others an absolute value threshold:

- Hemoglobin: treatment-emergent (TE) value 8.9 g/dL or less AND a decrease of 1 g/dL from Baseline
- Absolute Neutrophils: TE Neutrophils $<750/\text{mm}^3$, $<500/\text{mm}^3$ (2 thresholds) (Note: $1/\text{mm}^3 = 1/\mu\text{L} = 0.001 \times 10^3/\mu\text{L}$)
- Creatinine: TE $>2.5 \times \text{ULN}$ (reference range specific to gender/age)
- Alanine aminotransferase [ALT]: TE $>3 \times \text{ULN}$ (reference range specific to gender/age)
- Total bilirubin: TE $>3 \times \text{ULN}$ (reference range specific to gender/age)

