- Haptoglobin: $< \text{LLN}$

A listing of patients with positive direct antiglobin (DAT) test results (positive for at least one of IgG and C3) throughout the study will be provided that includes all DAT results for any patient with at least one positive DAT value, and all hemoglobin, absolute reticulocyte count, serum free hemoglobin, haptoglobin, LDH, and total and indirect bilirubin values at corresponding time points.

At Screening, a sample for HIV NAT testing will be collected and tested for determination of subject eligibility. The subject must be negative for HIV by NAT based on a Screening blood sample. The subject may enter the Previous Regimen Phase while the Screening blood sample is being tested, but will be a Screen Failure and will not undergo Baseline assessments if the HIV result is positive.

Virus safety (viral NAT and viral serology) retain samples will be collected at the Baseline/SC#1 Visit, but will be tested only if the subject exhibits clinical signs and symptoms consistent with viral infection while participating in the study. Virus safety samples will be retained until all analyses in support of the study are complete. Additional samples for viral NAT and viral serology testing may be collected and tested during the study only if the subject exhibits clinical signs and symptoms consistent with viral infection while participating in the study. If any virus safety testing was conducted, all available results will be listed.

All laboratory data will be presented in data listings.

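### By default the SAP leaves unscheduled and repeat draws out of its treatment-emergent laboratory threshold tables, so these tables can undercount by an amount the documents do not let us compute

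*SAP*

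**What the plan says.** SAP Section 4 sets the general rule in two consecutive sentences: "For table summaries, the data will be presented at the scheduled visits according to protocol". Then: "Any data collected at the unscheduled visits will be listed".

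SAP Section 11.2 describes three kinds of laboratory table:

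- Descriptive summaries of each parameter, given by visit.
- Shift tables: "Shift tables, based on the high/low flags, will also be summarized at each visit for each parameter with normal ranges".
- Threshold tables: "For selected analytes, tabular summaries and listings will be provided of treatment-emergent laboratory abnormalities utilizing the following thresholds of interest". The analytes are hemoglobin, absolute neutrophils, creatinine, ALT, total bilirubin and haptoglobin.

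The threshold sentence does not mention visits. It neither includes nor excludes unscheduled values, gives no rule for the worst post-Baseline value, and does not define a treatment-emergent laboratory value.

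Protocol Section 3.6.2 allows off-schedule contact: "Unscheduled visits may be conducted if deemed necessary for the purpose of subject safety". Footnote g of Protocol Appendix 1 places the safety laboratory panel after Baseline at "clinic visits coinciding with SC#13, #24, and #36, and the Final Visit". Protocol Section 3.6.2.7 gives the same panel at Early Termination.

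**The concern.** A threshold table answers a subject-level question: how many subjects crossed this limit at any time on treatment? A rule that admits only scheduled results suits means and changes by visit. Applied to an incidence table, it removes any crossing found between planned draws. Unscheduled visits are allowed for subject safety, so a result obtained at one is a plausible place for a crossing to appear.

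The study is single-arm, so no control arm is subject to the same omission. The tabulated number is itself the descriptive safety result. A reader of the tables would not know that the count leaves out some results unless they also worked through the listings.

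**Working it through.** The plan states no figure for laboratory abnormality counts, so there is nothing to reproduce. The check is mainly a reading of the text, with one illustration.

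**1. Which rule governs the threshold tables.** The Section 4 sentence on scheduled visits is unqualified. Neighbouring rules in Sections 4 and 4.1, on descriptive statistics, listings and missing observations, each begin by allowing for exceptions; this one does not. Section 11.2 ties the descriptive summaries and shift tables to visits but says nothing either way for the threshold tables. With no exception stated, a programmer would apply Section 4: an off-schedule crossing goes to the listing and is left out of the table. This exclusion is inferred from the general rule; Section 11.2 does not state it.

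**2. Whether off-schedule values are foreseeable.**

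- Protocol 3.6.2 permits unscheduled visits for safety.
- Protocol 4.2 includes laboratory tests in adverse event monitoring.
- Footnote a of Protocol Table 3-1 requires samples that cannot be analyzed to be drawn again, including hematology and chemistry. The SAP does not say whether such a repeat counts as scheduled.

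Neither document describes symptom-triggered hematology or chemistry. The symptom-triggered sampling that the SAP does name is virological ("Additional samples for viral NAT and viral serology testing may be collected and tested during the study only if" the subject has signs of viral infection). Those results are listed, and none is a threshold analyte.

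**3. Direction of any error.** Let S be the subjects with at least one crossing at a scheduled draw, and U those with at least one at an unscheduled or repeat draw.

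- Count under the Section 4 rule: |S|
- Count using all post-Baseline results: |S| + |U not in S|
- Difference: |U not in S|, which is zero or more

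The documents do not give |U not in S|. For scale only, with about 60 treated subjects as the denominator, each such subject is worth 1/60 = 1.7 percentage points.

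**4. How sparse the scheduled draws are.** Taking Week 1 as the start and draws at Weeks 13, 24, 36 and 53, the gaps are 13 − 1 = 12, 24 − 13 = 11, 36 − 24 = 12 and 53 − 36 = 17 weeks.

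Suppose an abnormality lasts d weeks and its onset is uniform over the 52 weeks from Week 1 to Week 53. Both are assumptions; the documents give no durations. A draw at week w sees the abnormality if onset falls in the d weeks up to w. For d no longer than the shortest gap (11 weeks) these four windows do not overlap, so

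P(present at a scheduled draw) = 4d/52

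- d = 1: 4/52 = 7.7%
- d = 2: 8/52 = 15.4%
- d = 4: 16/52 = 30.8%
- d = 8: 32/52 = 61.5%

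A grid calculation of the same quantity gave 0.077, 0.154, 0.308 and 0.615. It covers subjects who complete the study; the Early Termination panel is left out.

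**The case against.** The strongest reply is that Section 4 is a convention for by-visit displays and was never meant for subject-level incidence tables. It plainly does not govern every table: SAP 11.1 classifies adverse events by onset date and time, and SAP 8.1 classifies medications by their dates, whatever the visit type. A reader might infer that Section 4 keeps all unscheduled results out of all tables; the documents do not support that. The reply shows that the intent may be benign, but Section 11.2 still does not say so, and the unqualified rule is what remains.

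Second, Protocol 4.3.7 requires a laboratory abnormality that is clinically relevant, for example one that leads to withdrawal or treatment, to be reported as an adverse event, and SAP 11.1 then tabulates it. This stands and narrows the point. What can be missed is a numeric crossing, found only off schedule, that the investigator does not judge relevant. The threshold table exists to count such crossings without relying on that judgment.

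Third, nothing disappears from the report, because all laboratory data are listed. That is true, but a listing does not supply a count or a percentage.

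Fourth, a reader might take the complements of the figures for 2, 4 and 8 weeks (about 85%, 69% and 38%) as the share of abnormalities lost from the tables. They are not. Most such abnormalities would go unseen under either rule unless an extra draw happened to be taken, and the fix recovers only values actually drawn.

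Finally, these outputs are descriptive and no hypothesis rests on them. That limits the consequence, but the count should still be right.

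**Conclusion.** The point holds as a default that can undercount. As written, SAP Sections 4 and 11.2 would list but not count a subject whose only threshold crossing came from an unscheduled or repeat draw. Any error in the count runs one way, towards fewer abnormalities; the percentage follows if the denominator is fixed, such as the Safety population, which Section 11.2 does not spell out for these tables.

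It would go too far to say that the tables are biased in the product's favour. That needs an off-schedule hematology or chemistry result that crosses a limit in a subject with no scheduled crossing. The documents make such draws foreseeable but do not describe them or say how often they occur. The size of the undercount therefore cannot be computed and may be zero. The 4d/52 figures show only that four planned draws in a year leave room for off-schedule values to matter, under assumed durations and uniform onset.

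The change is still worth making before the tables are programmed: the rule is stated, its effect on these tables is unintended at best, and the correction is small.

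**What to change.** Add one sentence to SAP Section 11.2, along these lines:

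> The treatment-emergent threshold tables count a subject if any post-Baseline result, whether scheduled, unscheduled or repeat, meets the threshold, notwithstanding the scheduled-visit rule in Section 4.

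Keep the by-visit descriptive summaries and by-visit shift tables on scheduled visits, where the Section 4 rule is appropriate. A shift table from Baseline to the worst post-Baseline value would be a useful companion but is optional; its absence is not an error.

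The cost is the sentence and minor programming, with no new data collection. The abnormality counts can only stay the same or rise.
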